6 ELIGIBILITY CRITERIA

6.1 Inclusion criteria

- a. Age ≥18 years
- b. IgAN diagnosed on renal biopsy < 45 days
- c. PCR ratio >0.75 g/g (within 30 days before or after the renal biopsy)
- d. Renal biopsy with at least 8 glomeruli, disclosing at least 2 criteria among:
 - mesangial proliferation (according to Oxford criteria)
 - endocapillary proliferation (according to Oxford criteria)
 - tubulointerstitial fibrosis (according to Oxford criteria) >25% of the biopsy
 - segmental glomerulosclerosis (according to Oxford criteria)
 - ≥10% cellular/fibrocellular crescents.
- e. Patient with Social Security System Insurance or CMU
- f. Patient having signed an informed consent

6.2 Exclusion criteria

- a. >30% increase of serum creatinine within 15 days after starting RAS blockade therapy
- b. >50% cellular/fibrocellular crescents, or >50% tubulointerstitial fibrosis or >50% globally sclerotic glomeruli
- c. >50% plasma creatinine increase within the last 3 months before the renal biopsy
- d. Nephrotic syndrome with minimal change disease and IgA deposits
- e. eGFR <20 ml/min/1,73m² (CKD-EPI formula) within 30 days before or after the renal biopsy
- f. Uncontrolled blood pressure (Systolic blood pressure >180 mmHg or diastolic blood pressure > 110 mmHg)
- g. Previous corticosteroids treatment (>20 mg/d during more than 15 days, within the last 3 months before the renal biopsy)
- h. Pregnancy or breast feeding or women without sufficient contraception
- i. Secondary known forms of IgAN
- j. Henoch-Schoenlein purpura
- k. Additional other chronic renal disease
- Contraindication for immunosuppressive therapy, including active intestinal bleeding, active gastric or duodenal ulcer; active infection; any malignancy in a last years before the inclusion; severe psychiatric disease; living vaccines; anti-inflammatory dosages of acetylsalicylic acid
- m. Contraindication for RAS blockade therapy
- n. Known allergy or intolerance to corticoids or lactose

o. Organ transplant patient

The absence of measured GFR availability on the site is not an exclusion criterion.

6.3 Recruitment methods

About 20 diagnoses of primary IgAN are made each year in French tertiary nephrology centres. Among them, about 25% could be included in this protocol according to the inclusion and exclusion criteria, given the results of a retrospective study of 230 patients with IgAN diagnosed in Necker and HEGP hospitals in 2002-2008. 27 centres have already accepted to propose this protocol to their patients. Then, the expected number of inclusions could be reached in about 2 years.

7 TREATMENT ADMINISTERED TO RESEARCH PARTICIPANTS

7.1 Description of the experimental medications

For this study, two experimental medications will be administrated to the experimental group:

- 3 intravenous Methylprednisolone pulses (500 mg/pulse) will be administred during 3 successive one-day hospitalizations.
- oral corticosteroid treatment will be administred, during 4 months after the IV pulses, according to the following schedule and abacuses (see Annexe"1"):
- 1 mg/kg/d of prednisone during month 1 (begin at the D3 morning)
- 0.5 mg/kg/d of prednisone during month 2
- 0.25 mg/kg/d of prednisone during month 3
- 0.1 mg/kg/d of prednisone during month 4.

The maximum dose per day of prednisone is 80 mg.

Corticosteroids therapy is stopped at the end of the 4th month.

Corticosteroids dosage is rounded down to the closest multiple of 5 mg.

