9.2 Description of statistical methods to be used

All statistical analyses will be performed by Dr [name] (Paris Centre Clinical Research Department) using R software (http://cran.r-project.org).

Primary analyses will include all patients who underwent randomization and will be conducted on the intention-to-treat principle for efficacy outcomes and according to treatment received for toxicity end points. A per protocol analysis will be also performed, after exclusion of the subjects with at least one significant protocol deviation.

Descriptive analyses will be done for the two arms of treatment. Continuous variables will be summarized as mean (standard deviation) or median [range] and categorical variables as frequencies and percentages.

Primary end-point

Percentages of patient with failure at 24 months (as defined earlier) will be compared between groups using Chi2 test. Treatment effect will be presented as Relative Risk (RR) and its 95% CI.

Secondary end-points

Secondary efficacy and safety end points were analysed using Chi2 test (or Fisher's test if appropriate) and Student t test (or Wilcoxon test if appropriate).

To explore the emergence of any time-related patterns of response to treatment, means and 95% confidence intervals (CIs) for changes relative to baseline in proteinuria and GFR were plotted vs time from randomization until end of follow-up at 24 months. Means and 95% CIs for changes from baseline were compared at 6, 12 and 24 months using Student t test. In addition linear marginal regression models will be performed, if appropriate.

Three subgroups analyses are planned to explore whether the primary outcome results differed in particular groups of patients. Histological subgroups will be defined as the presence of mesangial proliferation or not, the presence of endocapilary proliferation or not and the presence of cellular or fibrocellular crescents or not. Log binomial regression models will be used for the subgroup analyses and will include terms for treatment group, subgroup, and the interaction between treatment group and subgroup. The interaction terms represent potential subgroup differences in treatment effects.

For efficacy and safety comparisons, P values of less than 0.05 were considered to indicate statistical significance.

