16.4 Abaques

Etude TIGER : Abaques prednisone

POSOLOGIE 1 mg/kg/jour

Poids (kg)	Dose en mg (poso 1mg/kg/j)	Arrondi dose (mg/jour)	Nb de cpr de 20 mg par jour	Nb de cpr de 5 mg par jour	Nb total de cpr par jour
30	30	30	1	2	3
31	31	30	1	2	3
32	32	30	1	2	3
33	33	35	1	3	4
34	34	35	1	3	4
35	35	35	1	3	4
36	36	35	1	3	4
37	37	35	1	3	4
38	38	40	2	0	2
39	39	40	2	0	2
40	40	40	2	0	2
41	41	40	2	0	2
42	42	40	2	0	2
43	43	45	2	1	3
44	44	45	2	1	3
45	45	45	2	1	3
46	46	45	2	1	3
47	47	45	2	1	3
48	48	50	2	2	4
49	49	50	2	2	4
50	50	50	2	2	4
51	51	50	2	2	4
52	52	50	2	2	4
53	53	55	2	3	5
54	54	55	2	3	5
55	55	55	2	3	5
56	56	55	2	3	5
57	57	55	2	3	5
58	58	60	3	0	3
59	59	60	3	0	3
60	60	60	3	0	3
61	61	60	3	0	3
62	62	60	3	0	3
63	63	65	3	1	4
64	64	65	3	1	4
65	65	65	3	1	4

Poids (kg)	Dose en mg (poso 1mg/kg/j)	Arrondi dose (mg/jour)	Nb de cpr de 20 mg par jour	Nb de cpr de 5 mg par jour	Nb total de cpr par jour
66	66	65	3	1	4
67	67	65	3	1	4
68	68	70	3	2	5
69	69	70	3	2	5
70	70	70	3	2	5
71	71	70	3	2	5
72	72	70	3	2	5
73	73	75	3	3	6
74	74	75	3	3	6
75	75	75	3	3	6
76	76	75	3	3	6
77	77	75	3	3	6
78	78	80	4	0	4
79	79	80	4	0	4
80	80	80	4	0	4
81	80	80	4	0	4
82	80	80	4	0	4
83	80	80	4	0	4
84	80	80	4	0	4
85	80	80	4	0	4
86	80	80	4	0	4
87	80	80	4	0	4
88	80	80	4	0	4
89	80	80	4	0	4
90	80	80	4	0	4
91	80	80	4	0	4
92	80	80	4	0	4
93	80	80	4	0	4
94	80	80	4	0	4
95	80	80	4	0	4
96	80	80	4	0	4
97	80	80	4	0	4
98	80	80	4	0	4
99	80	80	4	0	4
100	80	80	4	0	4
101	80	80	4	0	4
102	80	80	4	0	4
103	80	80	4	0	4
104	80	80	4	0	4
105	80	80	4	0	4
106	80	80	4	0	4

Poids (kg)	Dose en mg (poso 1mg/kg/j)	Arrondi dose (mg/jour)	Nb de cpr de 20 mg par jour	Nb de cpr de 5 mg par jour	Nb total de cpr par jour
107	80	80	4	0	4
108	80	80	4	0	4
109	80	80	4	0	4
110	80	80	4	0	4

POSOLOGIE 0,50 mg/kg/jour

Poids (kg)	Dose en mg (Poso 0,50 mg/kg/j)	Arrondi dose (mg/jour)	Nb de cpr de 20 mg par jour	Nb de cpr de 5 mg par jour	Nb total de cpr par jour
30	15	15	0	3	3
31	15,5	15	0	3	3
32	16	15	0	3	3
33	16,5	15	0	3	3
34	17	15	0	3	3
35	17,5	20	1	0	1
36	18	20	1	0	1
37	18,5	20	1	0	1
38	19	20	1	0	1
39	19,5	20	1	0	1
40	20	20	1	0	1
41	20,5	20	1	0	1
42	21	20	1	0	1
43	21,5	20	1	0	1
44	22	20	1	0	1
45	22,5	25	1	1	2
46	23	25	1	1	2
47	23,5	25	1	1	2
48	24	25	1	1	2
49	24,5	25	1	1	2
50	25	25	1	1	2
51	25,5	25	1	1	2
52	26	25	1	1	2
53	26,5	25	1	1	2
54	27	25	1	1	2
55	27,5	30	1	2	3
56	28	30	1	2	3
57	28,5	30	1	2	3
58	29	30	1	2	3

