Poids (kg)	Dose en mg (Poso 0,50 mg/kg/j)	Arrondi dose (mg/jour)	Nb de cpr de 20 mg par jour	Nb de cpr de 5 mg par jour	Nb total de cpr par jour
59	29,5	30	1	2	3
60	30	30	1	2	3
61	30,5	30	1	2	3
62	31	30	1	2	3
63	31,5	30	1	2	3
64	32	30	1	2	3
65	32,5	35	1	3	4
66	33	35	1	3	4
67	33,5	35	1	3	4
68	34	35	1	3	4
69	34,5	35	1	3	4
70	35	35	1	3	4
71	35,5	35	1	3	4
72	36	35	1	3	4
73	36,5	35	1	3	4
74	37	35	1	3	4
75	37,5	40	2	0	2
76	38	40	2	0	2
77	38,5	40	2	0	2
78	39	40	2	0	2
79	39,5	40	2	0	2
80	40	40	2	0	2
81	40	40	2	0	2
82	40	40	2	0	2
83	40	40	2	0	2
84	40	40	2	0	2
85	40	40	2	0	2
86	40	40	2	0	2
87	40	40	2	0	2
88	40	40	2	0	2
89	40	40	2	0	2
90	40	40	2	0	2
91	40	40	2	0	2
92	40	40	2	0	2
93	40	40	2	0	2
94	40	40	2	0	2
95	40	40	2	0	2
96	40	40	2	0	2
97	40	40	2	0	2
98	40	40	2	0	2
99	40	40	2	0	2

Poids (kg)	Dose en mg (Poso 0,50 mg/kg/j)	Arrondi dose (mg/jour)	Nb de cpr de 20 mg par jour	Nb de cpr de 5 mg par jour	Nb total de cpr par jour
100	40	40	2	0	2
101	40	40	2	0	2
102	40	40	2	0	2
103	40	40	2	0	2
104	40	40	2	0	2
105	40	40	2	0	2
106	40	40	2	0	2
107	40	40	2	0	2
108	40	40	2	0	2
109	40	40	2	0	2
110	40	40	2	0	2

POSOLOGIE 0,25 mg/kg/jour

Poids (kg)	Dose en mg (Poso 0,25 mg/kg/j)	Arrondi dose (mg/jour)	Nb de cpr de 20 mg par jour	Nb de cpr de 5 mg par jour	Nb total de cpr par jour
30	7,5	10	0	2	2
31	7,75	10	0	2	2
32	8	10	0	2	2
33	8,25	10	0	2	2
34	8,5	10	0	2	2
35	8,75	10	0	2	2
36	9	10	0	2	2
37	9,25	10	0	2	2
38	9,5	10	0	2	2
39	9,75	10	0	2	2
40	10	10	0	2	2
41	10,25	10	0	2	2
42	10,5	10	0	2	2
43	10,75	10	0	2	2
44	11	10	0	2	2
45	11,25	10	0	2	2
46	11,5	10	0	2	2
47	11,75	10	0	2	2
48	12	10	0	2	2
49	12,25	10	0	2	2
50	12,5	15	0	3	3
51	12,75	15	0	3	3

Poids (kg)	Dose en mg (Poso 0,25 mg/kg/j)	Arrondi dose (mg/jour)	Nb de cpr de 20 mg par jour	Nb de cpr de 5 mg par jour	Nb total de cpr par jour
52	13	15	0	3	3
53	13,25	15	0	3	3
54	13,5	15	0	3	3
55	13,75	15	0	3	3
56	14	15	0	3	3
57	14,25	15	0	3	3
58	14,5	15	0	3	3
59	14,75	15	0	3	3
60	15	15	0	3	3
61	15,25	15	0	3	3
62	15,5	15	0	3	3
63	15,75	15	0	3	3
64	16	15	0	3	3
65	16,25	15	0	3	3
66	16,5	15	0	3	3
67	16,75	15	0	3	3
68	17	15	0	3	3
69	17,25	15	0	3	3
70	17,5	20	1	0	1
71	17,75	20	1	0	1
72	18	20	1	0	1
73	18,25	20	1	0	1
74	18,5	20	1	0	1
75	18,75	20	1	0	1
76	19	20	1	0	1
77	19,25	20	1	0	1
78	19,5	20	1	0	1
79	19,75	20	1	0	1
80	20	20	1	0	1
81	20	20	1	0	1
82	20	20	1	0	1
83	20	20	1	0	1
84	20	20	1	0	1
85	20	20	1	0	1
86	20	20	1	0	1
87	20	20	1	0	1
88	20	20	1	0	1
89	20	20	1	0	1
90	20	20	1	0	1
91	20	20	1	0	1
92	20	20	1	0	1

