Poids (kg)	Dose en mg (Poso 0,25 mg/kg/j)	Arrondi dose (mg/jour)	Nb de cpr de 20 mg par jour	Nb de cpr de 5 mg par jour	Nb total de cpr par jour
93	20	20	1	0	1
94	20	20	1	0	1
95	20	20	1	0	1
96	20	20	1	0	1
97	20	20	1	0	1
98	20	20	1	0	1
99	20	20	1	0	1
100	20	20	1	0	1
101	20	20	1	0	1
102	20	20	1	0	1
103	20	20	1	0	1
104	20	20	1	0	1
105	20	20	1	0	1
106	20	20	1	0	1
107	20	20	1	0	1
108	20	20	1	0	1
109	20	20	1	0	1
110	20	20	1	0	1

POSOLOGIE 0,10 mg/kg/jour

Poids (kg)	Dose en mg (Poso 0,10 mg/kg/j)	Arrondi dose (mg/jour)	Nb de cpr de 20 mg par jour	Nb de cpr de 5 mg par jour	Nb total de cpr par jour
30	3	5	0	1	1
31	3,1	5	0	1	1
32	3,2	5	0	1	1
33	3,3	5	0	1	1
34	3,4	5	0	1	1
35	3,5	5	0	1	1
36	3,6	5	0	1	1
37	3,7	5	0	1	1
38	3,8	5	0	1	1
39	3,9	5	0	1	1
40	4	5	0	1	1
41	4,1	5	0	1	1
42	4,2	5	0	1	1
43	4,3	5	0	1	1
44	4,4	5	0	1	1

Poids (kg)	Dose en mg (Poso 0,10 mg/kg/j)	Arrondi dose (mg/jour)	Nb de cpr de 20 mg par jour	Nb de cpr de 5 mg par jour	Nb total de cpr par jour
45	4,5	5	0	1	1
46	4,6	5	0	1	1
47	4,7	5	0	1	1
48	4,8	5	0	1	1
49	4,9	5	0	1	1
50	5	5	0	1	1
51	5,1	5	0	1	1
52	5,2	5	0	1	1
53	5,3	5	0	1	1
54	5,4	5	0	1	1
55	5,5	5	0	1	1
56	5,6	5	0	1	1
57	5,7	5	0	1	1
58	5,8	5	0	1	1
59	5,9	5	0	1	1
60	6	5	0	1	1
61	6,1	5	0	1	1
62	6,2	5	0	1	1
63	6,3	5	0	1	1
64	6,4	5	0	1	1
65	6,5	5	0	1	1
66	6,6	5	0	1	1
67	6,7	5	0	1	1
68	6,8	5	0	1	1
69	6,9	5	0	1	1
70	7	5	0	1	1
71	7,1	5	0	1	1
72	7,2	5	0	1	1
73	7,3	5	0	1	1
74	7,4	5	0	1	1
75	7,5	10	0	2	2
76	7,6	10	0	2	2
77	7,7	10	0	2	2
78	7,8	10	0	2	2
79	7,9	10	0	2	2
80	8	10	0	2	2
81	8	10	0	2	2
82	8	10	0	2	2
83	8	10	0	2	2
84	8	10	0	2	2
85	8	10	0	2	2

Poids (kg)	Dose en mg (Poso 0,10 mg/kg/j)	Arrondi dose (mg/jour)	Nb de cpr de 20 mg par jour	Nb de cpr de 5 mg par jour	Nb total de cpr par jour
86	8	10	0	2	2
87	8	10	0	2	2
88	8	10	0	2	2
89	8	10	0	2	2
90	8	10	0	2	2
91	8	10	0	2	2
92	8	10	0	2	2
93	8	10	0	2	2
94	8	10	0	2	2
95	8	10	0	2	2
96	8	10	0	2	2
97	8	10	0	2	2
98	8	10	0	2	2
99	8	10	0	2	2
100	8	10	0	2	2
101	8	10	0	2	2
102	8	10	0	2	2
103	8	10	0	2	2
104	8	10	0	2	2
105	8	10	0	2	2
106	8	10	0	2	2
107	8	10	0	2	2
108	8	10	0	2	2
109	8	10	0	2	2
110	8	10	0	2	2

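### The prednisone rounding and cap stated in Protocol 7.1 do not produce the doses printed in the 16.4 tables

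*Protocol*

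**What the plan says.** Protocol 7.1 orders four months of oral prednisone after the pulses, "according to the following schedule and abacuses", so both the mg/kg schedule and the tables form part of the prescription. The schedule is 1, 0.5, 0.25 and 0.1 mg/kg/d in months 1 to 4; the last step reads "0.1 mg/kg/d of prednisone during month 4". Two general sentences follow: "The maximum dose per day of prednisone is 80 mg" and "Corticosteroids dosage is rounded down to the closest multiple of 5 mg". No weight cap and no other dose cap is given.

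Section 16.4 holds four tables, one per dose level, with a row for each kilogram from 30 to 110. Each row gives the calculated dose, the rounded daily dose and the tablet counts. The last three tables are headed "POSOLOGIE 0,50 mg/kg/jour", "POSOLOGIE 0,25 mg/kg/jour" and "POSOLOGIE 0,10 mg/kg/jour". Section 7.1 points to them as Annexe 1.

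Section 7.4.1 uses the same regimen for rescue in the control group. Section 9.2 plans a per-protocol analysis "after exclusion of the subjects with at least one significant protocol deviation".

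**The concern.** The two general sentences in 7.1 should describe how the tables were built, and they do not. Two separate things differ:

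- **Rounding.** The text rounds down; the tables go to the nearest 5 mg and send ties up. Taken literally, the text gives no prednisone in month 4 to anyone under 50 kg, against the same section's own order for that month.
- **Cap.** The text limits the daily dose to 80 mg. At 0.5 mg/kg that limit is not reached until 160 kg (80 / 0.5). The tables stop rising at 80 kg in every month, which the text nowhere mentions.

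At stake is the dose of the study drug, in the experimental arm and in rescue. A dose that is right by one source is wrong by the other in nearly half the entries, so pharmacists and monitors have no stated reference for a dosing deviation, and deviations feed the per-protocol exclusion in 9.2. Heavy patients are the second worry. Above 110 kg there is no table row, weight is not an exclusion in 6.2, and the text leads to doses in months 2 and 3 above the ceiling the tables apply to everyone else.

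**Working it through.** **Inputs.** Dose levels d = 1, 0.5, 0.25 and 0.1 mg/kg, the 80 mg cap and the rounding sentence (7.1); the printed doses for weights w = 30 to 110 kg (16.4). That is 81 weights × 4 months = 324 entries.

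**Step 1: reproduce the tables.** Nearest 5 mg, ties up, on capped weight: 5 × floor(d × min(w, 80)/5 + ½). This matches 81 of 81 entries in each table, 324 of 324 in all. The tables are therefore internally consistent and the differences are not extraction damage.

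**Step 2: apply the text of 7.1.** Rounded down, dose capped: 5 × floor(min(d × w, 80)/5).

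| Month (mg/kg) | Entries that differ | Table higher | Table lower |
|---|---|---|---|
| 1 (1) | 20 | 20 | 0 |
| 2 (0.5) | 46 | 25 | 21 (90–110 kg) |
| 3 (0.25) | 41 | 30 | 11 (100–110 kg) |
| 4 (0.1) | 45 | 45 | 0 |
| Total | 152 | 120 | 32 |

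Table minus text is +5 mg in 120 entries, −5 in 21, −10 in 10 and −15 in 1. So 120 + 21 = 141 differ by exactly 5 mg. The other 11 are all in month 2, at 100 kg or more. Within 50–110 kg, 104 of 61 × 4 = 244 entries differ (72 higher, 32 lower). All four months agree only at 60, 61 and 62 kg.

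**Step 3: worked rows.**

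| Weight, month | Calculated from d × w (mg) | Text (mg) | Table (mg) |
|---|---|---|---|
| 33 kg, month 1 | 33 | 30 | 35 |
| 35 kg, month 2 | 17.5 | 15 | 20 |
| 49 kg, month 4 | 4.9 | 0 | 5 |
| 75 kg, month 4 | 7.5 | 5 | 10 |
| 110 kg, month 2 | 55 | 55 | 40 |
| 110 kg, month 3 | 27.5 | 25 | 20 |

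**Step 4: lenient reading.** Suppose the sentence means nearest and keep only the 80 mg cap: 5 × floor(min(d × w, 80)/5 + ½). Months 1 and 4 then agree throughout. Month 2 still differs in 26 entries (85–110 kg) and month 3 in 21 (90–110 kg), 47 in all, and every one comes from the cap.

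**Step 5: four-month oral total**, assuming 30-day months.

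| Weight | Table (mg) | Text (mg) | Table against text |
|---|---|---|---|
| 58 kg | 30 × (60+30+15+5) = 3300 | 30 × (55+25+10+5) = 2850 | +16% |
| 78 kg | 30 × (80+40+20+10) = 4500 | 30 × (75+35+15+5) = 3900 | +15% |
| 100 kg | 4500 | 30 × (80+50+25+10) = 4950 | −9% |
| 110 kg | 4500 | 30 × (80+55+25+10) = 5100 | −12% |

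Over 50–110 kg the extremes are +16% (58 kg) and −12% (110 kg). Adding the pulses (3 × 500 = 1500 mg) to both sides, counted mg for mg as an assumption, gives 450/4350 = +10% at 58 kg, 600/5400 = +11% at 78 kg and −600/6600 = −9% at 110 kg.

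**Step 6: beyond the tables.** At 130 kg the text gives 65 mg in month 2 and 30 mg in month 3 (32.5 rounded down). The tables' rule would give 40 and 20 mg.

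**The case against.** The best answer is that sites will simply use the tables. Section 7.1 makes them part of the prescription, and they give a ready tablet count for each kilogram, whereas the conflicting rule is one loosely worded line in what looks like a translated protocol. Read as nearest, that line accounts for most of the 152 conflicts. The zero dose in month 4 contradicts the order beside it, so no site would sensibly follow it. Counting entries also weighs a 30 kg adult equally with a 70 kg one, and 48 of the 152 conflicts lie at 30–49 kg. Most differences are one 5 mg tablet a day. Section 9.2 removes only significant deviations, a term usually defined in the SAP, and a dose taken from the protocol's own table is unlikely to count as one. Actual doses are to be recorded under 3.3, so the exposure analyses would not have to rely on the nominal dose.

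Much of this stands, and it limits the severity: the effect on the per-protocol set is a possibility, not a forecast. It does not remove the defect. No sentence ranks the tables above the text, no reading of the rounding sentence supplies the missing 80 kg cap, and above 110 kg there is no table to fall back on. The plateau from 80 kg makes the intended extension fairly easy to guess, but a dosing rule should not rest on a guess.

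**Conclusion.** The concern holds and should be fixed. As written, 7.1 and 16.4 give different prednisone doses in 152 of 324 entries, and in 47 under the most generous reading. The usual size is 5 mg per day, with a maximum of 15 mg per day inside the tabulated range. The oral total differs by between +16% and −12% over 50–110 kg.

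The percentages assume 30-day months. The documents give no weight distribution, so these are counts of table entries and not of patients; how many patients would be affected cannot be stated. The intention-to-treat comparison, the composite endpoint and the sample size are untouched. What suffers is the definition of the experimental and rescue regimen, and with it the reference for judging dosing deviations.

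**What to change.** Replace the rounding and maximum-dose sentences in 7.1 with: *Prednisone is rounded to the nearest multiple of 5 mg (ties up), calculated on a weight of at most 80 kg (maximum 80/40/20/10 mg per day in months 1/2/3/4).* This reproduces all four tables exactly and covers patients above 110 kg.

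Before the change, the clinical and pharmacy leads should confirm that the tables are the intended regimen. In the same amendment, correct the Annexe 1 pointer to 16.4 and name the table dose (or, above 110 kg, the dose under the new sentence) as the reference for dosing deviations. The cost is a two-sentence amendment and a pharmacy memo, with no statistical cost.

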7.1.1 Methylprednisolone (IV)

Presentation :

- METHYLPREDNISOLONE 500 mg, powder for solution for injection (IV).

Storage :

Do not store above 25°C.

7.1.2 Prednisone (Per Os)

Presentation :

- PREDNISONE 20 mg, tablets
- PREDNISONE 5 mg, tablets

Storage ;

Prednisone does not require any special storage conditions.

7.1.3 Pharmaceutical circuit

Methylprednisolone and prednisone will be provided by clinical trial department of AGEPS (Agence Générale des Equipements et Produits de Santé) that will ensure the secondary

labelling according to the good manufacturing practices, and the supply to the pharmacy of each clinical site according to the good distributing practices.

Experimental drugs will be stored by the pharmacies. Dispensing will be made on presentation of a specific nominative prescription of the study.

7.2 Description of the non-experimental treatments

7.2.1 Non-experimental medication used in corticosteroidstreated patients

Prophylaxis against glucocorticoid-induced osteoporosis with bisphosphonate therapy is recommended during the treatment with corticosteroids. Alendronate or risedronate could be used according to local practices.

Calcium supplementation is recommended to achieve a minimum total calcium intake of 1200 mg/day.

Prophylaxis against glucocorticoid-induced Pneumocystis jiroveci (formerly P. carinii) pneumonia infections should include sulfamethoxazole-trimethoprim as a single strength tablet daily (i.e. 480 mg daily) or a double strength tablet every other day thrice weekly (i.e. 960 mg Monday, Wednesday, and Friday). In case of intolerance or allergy to sulfamethoxazole-trimethoprim, atovaquone treatment or pentamidine aerosols are recommended. The use of this Pneumocystis jiroveci prophylaxis is left to the discretion of local investigators.

Prophylaxis against strongyloides hyperinfection with ivermectine is recommended before starting corticosteroids in case of potential previous strongyloides exposure.

Peptic ulcer prophylaxis with proton pump inhibitors is recommended and is left to the discretion of the patient physician.

The use of other prophylactic therapies will be left to local practice and the discretion of local investigators.

Dietary regimen (RENIF file) and lifestyle counseling is provided during consultations or hospitalization, for avoiding high simple carbohydrates-diet while treated with corticosteroids.

7.2.2 Non-experimental medication used in all patients

The following treatments are part of current recommendations for IgAN treatment.

Vitamin D supplementation is recommended for all patients according to the patient physician discretion, with a minimum vitamin D administration equivalent to colecalciferol: 100000 UI each 3 months.

Dietary regimen and lifestyle counseling is provided during consultations or hospitalization, with the following objectives:

- Avoiding high protein intake (>1,3 g/kg/d)
- Lowering salt intake to <90 mmol/d of sodium (corresponding to 5 g of sodium chloride)
- Undertaking physical activity compatible with cardiovascular health and tolerance
- Achieving a healthy weight (BMI 20 to 25)
- Stop smoking.

Treatment with RAS blockade therapy (one molecule or in association) is systematically administred in all patients.

RAS blockade with ACE-inhibitors or angiotensin receptor blockers is initiated using the drug chosen by the patient physician. Low dosage is initiated if eGFR is <45 ml/min/1,73m².

Medium dosage is initially used if eGFR is >45 ml/min/1,73m². Every modification of RAS blockade is followed by a control of plasma creatinine and potassium within 3 weeks. These results can lead to diminution or interruption of RAS blockade according to local decision. RAS blockade should be increased at each visit to achieve the following objectives, according to the patient physician decision:

- Blood pressure <130/80 mmHg while sitting
- PCR <0,5 g/g or PCR <0.75 g/g and <30% of initial PCR

Patients can be converted to an ARB when an ACE-inhibitor is not tolerated. Dose equivalence tables for ACE-inhibitors and ARB's will be provided. Bitherapy with ACE inhibitors and ARB is allowed. All other antihypertensive medications, including diuretics, calcium-channel blockers and ß-blocker can be used at any time-point during the study depending on the clinical decision of the patient physician.

Hyperkalemia is treated according to current guidelines.

